8.2 CLASSIFICATION OF AN ADVERSE EVENT

8.2.1 SEVERITY OF EVENT

For AEs not included in the protocol-defined grading system, the following guidelines will be used to describe severity.

- **Mild** – Events require minimal or no treatment and do not interfere with the participant's daily activities.
- **Moderate** – Events result in a low level of inconvenience or concern with the therapeutic measures. Moderate events may cause some interference with functioning.
- **Severe** – Events interrupt a participant's usual daily activity and may require systemic drug therapy or other treatment. Severe events are usually potentially life-threatening or incapacitating.

8.2.2 RELATIONSHIP TO STUDY INTERVENTION

Because this is an imaging study, where no clinical decision will be altered, we will only record AEs that have to do with the research procedures. The three research procedures are the pre-treatment, post-first fraction and post-treatment DCE-CT imaging.

8.2.3 EXPECTED ADVERSE EVENTS

The Investigator will be responsible for determining whether an SAE is expected or unexpected. An SAE will be considered unexpected if the nature, severity, or frequency of the event is not consistent with the risk information previously described for the study agent.

8.3 TIME PERIOD AND FREQUENCY FOR EVENT ASSESSMENT AND FOLLOW-UP

The occurrence of an AE or SAE may come to the attention of study personnel during study visits and interviews of a study participant presenting for medical care, or upon review by a study monitor. All AEs including local and systemic reactions not meeting the criteria for SAEs will be captured on the appropriate CRF. Information to be collected includes event description, time of onset, clinician's assessment of severity, relationship to study product (assessed only by those with the training and authority to make a diagnosis), and time of resolution/ stabilization of the event. All AEs occurring while on study must be documented appropriately. All AEs will be followed to adequate resolution.

The PI will record all reportable events with start dates occurring any time after informed consent is obtained until the last study visit. At each study visit, the investigator will inquire about the occurrence of AE/ SAEs since the last visit. Events will be followed for outcome information until resolution or stabilization.

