Subjects will complete radiation therapy in 1 to 2 weeks, depending on prescribed radiation dose. This is the SOC with no modifications to the radiation treatment characteristics.

Step 5 (Six-week follow-up/Post-treatment perfusion assessment):

Subjects will have a follow-up visit with the radiation oncologist approximately 6 weeks after the completion of radiation therapy. DCE-CT imaging will be performed at this time to assess perfusion. This perfusion measure will be for outcome assessment of radiation effects. This DCE-CT imaging will be for research purposes.

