7 STUDY PROCEDURES AND SCHEDULE

7.1 STUDY PROCEDURES/EVALUATIONS

1. Subject enrollment and initial visit with radiation oncologist

The subject will have a pre-treatment, standard of care work-up visit with the radiation oncologist. During this visit, the study team will explain the study to the patient and obtain informed consent. After consent has been obtained, the study team will assess if the subject meets study criteria and can be enrolled into the study.

2. Pre-treatment DCE-CT Imaging

During the initial CT simulation process, the pre-treatment perfusion imaging will be obtained using DCE-CT. The initial CT simulation process is used to create the radiation therapy treatment plan and is a part of SOC. At the end of the CT simulation session, additional DCE-CT imaging will be acquired.

3. Delivery of Radiation Therapy

Treatment will be performed on a linear accelerator with on-board imaging capabilities to align the subject to the same treatment position for every treatment session. Throughout treatment, the subject will have a weekly evaluation with the radiation oncologist to help manage any health problems that may arise.

Subjects will have DCE-CT imaging within six hours of receiving the first fraction of radiation therapy to assess the SBRT related changes to baseline perfusion characteristics.

4. Six week follow-up visit/Post-treatment DCE-CT Imaging

The subject will have a SOC six week follow-up visit with the radiation oncologist. During the consult, the radiation oncologist will assess any issues arising from radiation treatment. At this

consult, the subject will also undergo their final session of DCE-CT imaging to assess perfusion changes after completion of radiation therapy.

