7.2.4 FINAL STUDY VISIT

- Record adverse events as reported by participant or observed by investigator if related to DCE-CT.

- Record participant's adherence to treatment program.

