8 ASSESSMENT OF SAFETY

8.1 SPECIFICATION OF SAFETY PARAMETERS

8.1.1 DEFINITION OF ADVERSE EVENTS (AE)

Adverse event means any untoward medical occurrence associated with the use of an intervention in humans.

Because this is an imaging study, where no clinical decision will be altered, we will only record AEs that have to do with the research procedures. The three research procedures are the pre-treatment, post-first fraction, and post-treatment DCE-CT imaging.

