8.6 SAFETY OVERSIGHT

Monitoring and Oversight

The sponsor investigator will be responsible for monitoring the trial per the trial monitoring plan, in addition to overseeing the safety and efficacy of the trial including any specimens collected, executing the data and safety monitoring (DSM) plan, and complying with all reporting requirements to local and federal authorities. This oversight will be accomplished through additional oversight from the Data and Safety Monitoring Committee (DSMC) at the University of Colorado Cancer Center (CU Cancer Center). The DSMC is responsible for ensuring data quality and study participant safety for all clinical studies at the CU Cancer Center, which is the coordinating institution of this trial. A summary of the DSMC's activities is as follows:

- Conduct of internal audits
- Ongoing review of all serious adverse events (SAEs), unanticipated problems (UAPs) and reportable adverse events (AEs)
- Has the authority to close and/or suspend trials for safety or trial conduct issues

- May submit recommendations for corrective actions to the CU Cancer Center's Executive Committee

Per the CU Cancer Center Institutional DSM Plan, SAEs, UAPs and reportable AEs are reported to the DSMC, IRB and the sponsor investigator per protocol. All SAEs, UAPs and reportable AEs are to be reported to the DSMC within 5 business days of the sponsor investigator receiving notification of the occurrence.

Study audits conducted by the DSMC will consist of review of the regulatory records, consent forms and source data verification. Documentation of the audit conducted by the DSMC will then need to be submitted to the IRB of record at the time of the IRB's continuing review of this trial.

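### Section 8.3 stops recording events at the last scheduled visit, the day of the third DCE-CT, so scan-related events that start later have no recording window and no scheduled enquiry

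*Combined protocol and SAP*

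**What the plan says.** Section 8.1.1 confines safety recording to the three research scans: "we will only record AEs that have to do with the research procedures". Section 8.3 then sets the time limits. Reportable events are recorded "with start dates occurring any time after informed consent is obtained until the last study visit". They are sought actively only at visits: "At each study visit, the investigator will inquire about the occurrence of AE/ SAEs since the last visit". Section 8.3 also accepts that an event may surface "during study visits and interviews of a study participant presenting for medical care, or upon review by a study monitor".

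The third scan is part of the 6-week follow-up. Section 7.1 says that at this consult "the subject will also undergo their final session of DCE-CT imaging to assess perfusion changes after completion of radiation therapy", and Step 5 of section 4.1 agrees: "DCE-CT imaging will be performed at this time to assess perfusion". In the 7.2.7 table the adverse-event row is marked at baseline, mid-treatment and 6 weeks, and the 6-week column is the last.

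Section 7.2.4 has a separate heading for a Final Study Visit. It lists no scan and gives no date, and asks staff to: "Record adverse events as reported by participant or observed by investigator if related to DCE-CT".

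Reporting duties are set out elsewhere. Section 8.6 states: "All SAEs, UAPs and reportable AEs are to be reported to the DSMC within 5 business days of the sponsor investigator receiving notification". Sections 8.4.3 and 8.5 cover unanticipated problems and the halting rule.

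**The concern.** When scan-related events are the only adverse events a study records, one expects the recording window to outlast the last scan. Here the window appears to close on the day of that scan. A participant who develops symptoms some days after scan one or scan two will be asked about them at a later visit. A participant with the same symptoms after scan three will not be asked, and the start date would fall outside section 8.3 even if the event became known.

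The consequence is limited but real. Finding no late events after scan three would carry less information than finding none after the first two scans. Section 2.3.1 names contrast-induced nephropathy as possibly the more important contrast risk. If it caused symptoms after the visit day, it would be an event of the kind described here. That timing is an assumption, because the section gives no onset times.

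**Working it through.** The plan states no figure on this point, so there is nothing to reproduce. The check sets the window against the visit schedule.

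**Inputs**
- SBRT lasts 1 to 2 weeks (4.1, Step 4).
- Scan one takes place 0 to 3 weeks before the first fraction (7.2.7).
- Scan two takes place within six hours of the first fraction (4.1, 7.1, 7.2.3). The 7.2.7 table instead allows any time between the first and last fractions.
- Scan three takes place at the 6-week visit. The allowed range after SBRT is 4 to 8 weeks in 4.1, 5 to 7 weeks in 7.2.3, and 4 to 6 weeks in 7.2.7.
- Enrolment is 10 to 15 participants (10.5).

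**Time from each scan to the end of the 8.3 window, if the 6-week visit is the last visit**

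The widest follow-up range (4 to 8 weeks) is used:
- Scan one: 0 + 1 + 4 = 5 weeks, to 3 + 2 + 8 = 13 weeks.
- Scan two on the day of the first fraction: 1 + 4 = 5 weeks, to 2 + 8 = 10 weeks. If it can be as late as the last fraction, the minimum is 0 + 4 = 4 weeks.
- Scan three: the rest of the visit day only.

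The narrower follow-up ranges change the figures for scans one and two but not the result for scan three.

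**Scheduled enquiries after each scan visit (7.2.7 adverse-event row)**
- Scan one: 2 (mid-treatment and 6 weeks).
- Scan two: 1 (6 weeks).
- Scan three: 0.

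The weekly on-treatment evaluations in 7.1 may add contacts after scans one and two. They cannot add any after scan three.

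**Exposures concerned, if everyone completes**
- Research injections: 3 × 10 = 30, to 3 × 15 = 45.
- Scan-three injections: 10 to 15, which is 10/30 = 15/45 = one third.

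These figures describe the schedule. They do not measure risk.

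**What each provision does for an event that starts after the 6-week visit day**
- 8.3, window: excludes it by start date.
- 8.3, enquiry: none is scheduled, because no later visit exists in 7.2.7.
- 8.3 and 8.4.2, follow-up to resolution or stability: sets how long an event is followed, and does not lengthen the start-date window.
- 8.4.3, 8.5 and 8.6: set no start-date limit of their own, so they reach the event if someone reports it. They do not provide for anyone to ask.

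**The case against.** **The Final Study Visit may be a later visit.** Section 7.2.3 already holds the 6-week scan with its own event recording, and 7.2.4 repeats that recording under a separate heading with no scan. If 7.2.4 is a distinct later visit, the window and the enquiry both extend past scan three. The 7.2.7 table and 7.1 favour a single visit, because nothing follows the 6-week consult in either. The doubt is not fully removed: the schematic is not shown, and the procedures manual and data and safety monitoring plan are not available. This part of the objection stands as a reason to date 7.2.4.

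**Late events are not lost to oversight.** A reader might infer that a late serious event after scan three could not be reported or could not count towards halting. The documents do not support that. The duties in 8.4.3 and 8.6 turn on the investigator's responsibility and on receipt of notification, and 8.5 counts related grade 3 events once they are reported to the clinician. This stands. What remains is the absence of an enquiry and of recording under 8.3.

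**The risk is not quantified.** Section 2.3.1 describes contrast reactions as mostly mild and short-lived. A reader might apply its nephropathy incidences (2%, or about 30% with chronic renal impairment) to 10 to 15 participants and obtain 0.2 (10 × 0.02) to 4.5 (15 × 0.30) cases missed after scan three. That is not supported. Those incidences are not restricted to cases with symptoms or to onset after the visit day, and the upper end requires every participant to have chronic renal impairment. Section 7.2 lists no renal test at any visit, so nephropathy without symptoms could go unseen after any of the scans and is a separate matter.

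**No analysis is affected.** Safety is not a listed objective or endpoint, and no comparison of events by scan is planned. This is correct, and it limits the severity.

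**Conclusion.** The point holds as a minor one. On the text available, section 8.3 excludes DCE-CT-related events that start after the 6-week visit day, and no one is scheduled to ask about them. Scans one and two are each followed by at least one later visit that asks. The gap applies to one injection in three if all participants complete, and mainly to events that nobody volunteers. Reactions on the day of scan three can still be recorded.

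The conclusion rests on reading the 7.2.4 visit as the 6-week visit, and on no later contact being specified in material that is not available. The clinical yield is unknown, because the documents give neither onset times nor a rate of delayed reactions.

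A reader might also see a conflict between 5.4.2, which provides no follow-up of completed or withdrawn participants, and the follow-up duties in 8.3 and 8.4.2. Section 5.4.2 can be read as covering outcome follow-up only, so no conflict is claimed.

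**What to change.** 1. In 8.3, record DCE-CT-related events with start dates up to the later of the last study visit and a fixed short period after the participant's last DCE-CT. Seven days is offered as a default. It is an assumption that the sponsor may adjust, since the documents supply no basis for a length.
2. Add one phone enquiry at the end of that period, unless consent has been withdrawn.
3. In 7.2.4, state that the Final Study Visit is the 6-week visit. If a later visit is intended, give its date and add it to 7.2.7.

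Optionally, add a sentence to 5.4.2 saying that DCE-CT-related events still open at completion or removal are followed under 8.3 and 8.4.2 unless consent is withdrawn.

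The cost is at most 15 phone calls (one for each of up to 15 participants), a protocol amendment approved by the IRB (13.2), and possibly a consent-form update, because 13.3 requires the form to describe study length and follow-up. No scan, laboratory test, clinic visit or staff post is added.

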8.4 REPORTING PROCEDURES

8.4.1 ADVERSE EVENT REPORTING

Reporting of UAPs, SAEs, and reportable AEs will be performed pursuant to the UCCC DSMC and IRB institutional policy.

8.4.2 SERIOUS ADVERSE EVENT REPORTING

All SAEs will be followed until satisfactory resolution or until the PI deems the event to be chronic or the adherence to be stable.

SAEs will be reported pursuant to section 8.6.

8.4.3 UNANTICIPATED PROBLEM REPORTING

This study will follow COMIRB's guidance for UAP reporting and the DSMC's requirements (discussed in section 8.6). AEs, noncompliance and protocol violations will be recorded and reported as required either promptly (within 5 days of Sponsor-Investigator's knowledge) or at the time of the study's continuing review.

It is the responsibility of the PI to report incidents or events that meet the criteria for UAPs reporting to their IRB using the IRB's standard UAP form. The PI is responsible for reporting the UAP to the UCCC DSMC, if applicable.

8.5 STUDY HALTING RULES

Administration of a study intervention will be halted when three grade 3 AEs related to DCE-CT that are determined to be at least "probably related" are reported to the clinician. The clinician will notify the study sponsor and PIs immediately when the third grade 3 event is reported and enrollment screens will stop accepting new study participants. The study sponsor will inform the UCCC DSMC members within 24 hours of this occurrence and will provide the UCCC DSMC with AE listing reports. The UCCC DSMC will convene an *ad hoc* meeting by teleconference or in writing as soon as possible. The DSMB will provide recommendations for proceeding with the study to the study sponsor. The study sponsor will inform the FDA of the temporary halt and the disposition of the study, if applicable.

8.6 SAFETY OVERSIGHT

Monitoring and Oversight

The sponsor investigator will be responsible for monitoring the trial per the trial monitoring plan, in addition to overseeing the safety and efficacy of the trial including any specimens collected, executing the data and safety monitoring (DSM) plan, and complying with all reporting requirements to local and federal authorities. This oversight will be accomplished through additional oversight from the Data and Safety Monitoring Committee (DSMC) at the University of Colorado Cancer Center (CU Cancer Center). The DSMC is responsible for ensuring data quality and study participant safety for all clinical studies at the CU Cancer Center, which is the coordinating institution of this trial. A summary of the DSMC's activities is as follows:

- Conduct of internal audits
- Ongoing review of all serious adverse events (SAEs), unanticipated problems (UAPs) and reportable adverse events (AEs)
- Has the authority to close and/or suspend trials for safety or trial conduct issues

- May submit recommendations for corrective actions to the CU Cancer Center's Executive Committee

Per the CU Cancer Center Institutional DSM Plan, SAEs, UAPs and reportable AEs are reported to the DSMC, IRB and the sponsor investigator per protocol. All SAEs, UAPs and reportable AEs are to be reported to the DSMC within 5 business days of the sponsor investigator receiving notification of the occurrence.

Study audits conducted by the DSMC will consist of review of the regulatory records, consent forms and source data verification. Documentation of the audit conducted by the DSMC will then need to be submitted to the IRB of record at the time of the IRB's continuing review of this trial.

9 CLINICAL MONITORING

Clinical site monitoring will be conducted to ensure that the rights and well-being of human participants are protected, that the reported trial data are accurate, complete, and verifiable, and that the conduct of the trial is in compliance with the currently approved protocol/ amendment(s), with GCP, and with applicable regulatory requirement(s).

Monitoring for this study will be performed by a CU Cancer Center Clinical Monitor in accordance with the clinical monitoring plan (CMP), incorporated herein by reference. The CMP describes in detail who will conduct the monitoring, at what frequency monitoring will be done, at what level of detail monitoring will be performed, and the distribution of the monitoring reports.

Independent audits will be conducted by the CU Cancer Center DSMC to ensure monitoring practices are performed consistently across all participating sites, if applicable, and that monitors are following the CMP.

10 STATISTICAL CONSIDERATIONS

10.1 STATISTICAL AND ANALYTICAL PLANS

The utility of perfusion falls under two categories: predictive performance from DCE-CT imaging changes, and outcome assessment of radiation therapy treatment. Perfusion will be characterized for a number of different parameters from a pharmacokinetic model. Multiple pharmacokinetic models can describe perfusion. For completeness, we will examine several models including: tissue homogeneity, Tofts, extended Tofts, and Patlak. Model goodness of fit will be assessed with root mean square error. The following perfusion parameters, derived from previously mentioned

pharmacokinetic models, will be quantified for each DCE-CT session: blood flow, blood volume of vascular space, blood volume of extracellular space, and intra-compartment plasma flow. For each model, these perfusion parameters will have the mean, extrema, and standard deviation of each parameter value calculated.

Treatment response will be assessed using the DCE-CT imaging changes from the baseline to the 6-week follow-up. Changes in perfusion parameters will be compared to the delivered dose with correlation coefficients, logistic regression analysis, and receiver operating characteristic analysis.

10.2 STATISTICAL HYPOTHESES

- Primary Efficacy Endpoint(s):
No formal hypothesis testing will be conducted for the primary analysis

10.3 ANALYSIS DATASETS

All participants who completed their baseline DCE-CT scan, had at least one radiation therapy treatment and one follow-up DCE-CT scan will be included in the analysis dataset to assess change in perfusion measurements from baseline to first follow-up. The analysis dataset for change in perfusion metrics at 6 weeks will include participants who completed their radiation treatment and have both baseline and 6-week DCE-CT scans.

10.4 DESCRIPTION OF STATISTICAL METHODS

10.4.1 GENERAL APPROACH

How profusion metrics change following SBRT treatment is unknown. Therefore, this is a prospective, pilot study is primarily aimed at gathering preliminary data on profusion metrics and assessing the relationship between change in profusion and radiation dose delivered from SBRT. Due to the limited knowledge on how radiation therapy will affect profusion metrics, change in profusion metrics following therapy will be assessed both after a patient's first treatment and at 6-weeks following their end of the SBRT treatment. Descriptive statistics will be provided for all measured variables.

10.4.2 ANALYSIS OF THE PRIMARY EFFICACY ENDPOINT(S)

The primary endpoint of this study is change in profusion metrics from baseline to end of first radiation treatment and 6-weeks after treatment has ended. Additionally, total radiation dose delivered from SBRT will be captured and used as a surrogate measurement for treatment response.

Individual profusion metrics will be plotted as well as means with corresponding standard errors for the three time points. Change in profusion metrics from baseline versus radiation dose received will be plotted separately for the two follow-up DCE-CT scans. Correlation between change in profusion and total radiation dose received will be evaluated using Spearman's correlation coefficient.

